9.3.1.3 Prior and Concomitant Medications and Vaccinations

Prior and concomitant medications and vaccinations will be summarized overall and by vaccine group and preferred drug name as coded using the World Health Organization (WHO) drug dictionary for all participants on the Safety Analysis Set.

9.3.1.4 Extent of Exposure

The number of participants receiving study vaccine will be presented by vaccine group on the Safety Analysis Set. Below information will also be summarized by vaccine group: whether the vaccine is administered and the reason if not, whether the vaccine is administered per protocol and the reason if not, whether full dose is administered and the reason if not, anatomical location of the administration, follow-up time since the first vaccination.

9.3.1.5 Vital Sign Measurements and Physical Examination

Listings will be provided for vital sign measurements and physical examinations data collected.

9.3.2 Immunogenicity Analysis

All immunogenicity analyses will be descriptive. Listings will be provided for all immunogenicity data collected.

9.3.2.1 Analysis of Primary Immunogenicity Endpoints

The analysis of the primary immunogenicity endpoints will be performed using the Per-Protocol (PP) Analysis Set and the Neutralization Assay Subset.

The primary immunogenicity endpoints focus on NAb against the Omicron XBB1.5 strain at Day 28 following initial study vaccination. Neutralizing antibodies (NAb) GMT and GMFR (compared to Day 0) to the Omicron XBB.1.5 strain and corresponding 95% CIs, are summarized at Day 28 by vaccine group. GMT is calculated as the antilog of the mean of log-transformed titer values. GMFR is the antilog of the mean of log-transformed fold-rises. The 95% CIs are calculated based on the t-distribution of the log transformed titer or fold-rise values, then back transformed to the original scale. The between-group ratio of GMT (GMTR) at Day 28 and the two-sided 95% CIs are computed using the analysis of covariance with the vaccine group as the fixed effect and the titer at Day 0 (ie, adjusted for intergroup variation in baseline [pre-vaccination] titers) as the covariate. The mean difference between vaccine groups and the corresponding 95% CIs. There is no formal evaluation of statistical hypotheses.

Seroresponse is defined as post-vaccination titer \geq 4-fold increase from baseline value. Participants with a baseline value below the lower limit of quantitation (LLOQ) will be considered achieving seroresponse only if the post-baseline value is greater than or equal to 4 times the LLOQ. The percentage of participants achieving seroresponse rate (SRR) is calculated at Day 28. 95% CIs of the SRR will be calculated based on the exact Clopper-Pearson method. Difference in SRR will be calculated at Day 28, with the 95% CI for the difference based on the method of Miettinen and Nurminen.

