	• NAb titers and IgG GMEUs to the ancestral (Wuhan) strain at relevant time points (Days 0, 28, 90, and 180). Derived/calculated endpoints based on these data will include GMFR.
	Objective : To describe antibody responses in a human angiotensin converting enzyme-2 (hACE2) receptor binding inhibition assay induced by NVX-CoV2601 and the bivalent vaccine (NVX-CoV2373 + NVX-CoV2601) to the Omicron XBB.1.5 and ancestral (Wuhan) strains over time.
	Endpoints:
	 GMTs to the Omicron XBB.1.5 and ancestral (Wuhan) strains at relevant time points (Days 0, 28, 90, and 180). Derived/calculated endpoints based on these data will include GMFR.
	Objective: To describe antibody responses in a mucosal IgA-mediated hACE2 receptor binding inhibition assay induced by NVX-CoV2601 and the bivalent vaccine (NVX-CoV2373 + NVX-CoV2601) to the Omicron XBB.1.5 and ancestral (Wuhan) strains over time.
	Endpoints:
	• GMTs to the Omicron XBB.1.5 and ancestral (Wuhan) strains at relevant time points (Days 0 and 28). Derived/calculated endpoints based on these data will include GMFR.
	Objective: To utilize additional assays (current or to be developed) to better characterize the immune response for future vaccine development needs.
	Endpoint: Additional endpoints to evaluate immune responses may be developed based on the assays used.
	Objective: To characterize the severity of COVID-19 in participants who become infected during the course of the study.
	Endpoint: Detected case will be characterized as mild, moderate, or severe as assessed using the provided criteria.
Number of Sites	Up to 25 sites in the United States and Canada (Canadian sites contingent upon additional approval).
Study Duration	Estimated duration: Approximately 7 months
	1

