7.2.2 Randomization Strategy and Procedure

Randomization will take place on Day 0 after confirmation that the participant meets the inclusion/exclusion criteria.

Eligible participants will be randomized 1:1 to Group A or Group B (approximately 200 participants each). Randomization will be stratified by number of prior mRNA COVID-19 vaccinations received and site.

Within each study site, participants will be randomized to study treatment according to a list produced by Syneos. Prior to production, the randomization specification will be reviewed and

SARS-CoV-2 rS Vaccines	Study Protocol 2019nCoV-314 Amen	dment 2 v4.0
Novavax	Confidential	Page 47

agreed to by the study team (the Sponsor and Syneos). Block size is considered potentially unblinding information and will only be known by unblinded study personnel.

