9.2.4 Per-Protocol Analysis Set

The Per-Protocol (PP) Analysis Set will be determined for each strain, serology assay and study visit. The PP Analysis set will include all participants who receive the full prescribed regimen of the study vaccine up to the visit according to protocol, have serology results for baseline and the time point analyzed, are PCR negative at baseline for SARS-CoV-2, and have no major protocol violations or an event (eg, COVID-19 infection) that are considered clinically relevant to impact immunogenicity response as determined prior to database lock.

Within the PP Analysis Set there are 3 subsets defined:

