9.4.1.2 Demographics and Baseline Characteristics

Baseline demographic and background characteristics (eg, age, gender, ethnicity, race, height, weight, and BMI [derived]) will be summarized by vaccine group for the FAS, Safety, and PP Analysis Sets. Frequencies and percentages will be presented for categorical variables. Continuous variables will be summarized using descriptive statistics (total number of participants, mean and standard deviation, median, minimum, and maximum).

Medical history will be coded using MedDRA terms. Baseline medical history recorded at Screening will be summarized by the study vaccine group and by MedDRA SOC/PT for all participants in the Safety Analysis Set. Within each SOC and PT, the number and percentage of participants with at least one medical history event will be presented, respectively. Multiple events within a given SOC and PT for a participant will be counted once.

The characterization of baseline immunity will be summarized, to include tabulation of PCR and anti-N results at Day 0, the brand(s) of mRNA vaccine previously received, the number of doses received, and the length of the interval between last mRNA vaccine and study investigational vaccine.

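### The ANCOVA for the Day 28 GMT ratio omits both randomization strata, so its confidence interval may be slightly wider than it needs to be

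*Protocol*

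**What the plan says.** - **Randomization (Section 7.2.2):** "Randomization will be stratified by number of prior mRNA COVID-19 vaccinations received and site". Allocation is 1:1, about 200 per group. The Synopsis plans "Up to 25 sites in the United States and Canada".
- **Model (Section 9.3.2.1):** for Day 28, the GMT ratio and its interval "are computed using the analysis of covariance with the vaccine group as the fixed effect and the titer at Day 0" as covariate. Neither stratification factor appears here or in any other model in the protocol, and no reason is given.
- **Who fixes the model:** Sections 9.3.2.3 and 9.3.3 leave other exploratory analyses to the SAP. The GMT ratio model is written out in the protocol itself, and Section 9.7 treats any departure as a change to be documented.
- **Relevance of dose count:** Section 9.4.1.2 lists "the brand(s) of mRNA vaccine previously received, the number of doses received, and the length of the interval" since the last dose when it characterizes baseline immunity.
- **Status of the analysis (Section 9.3.2):** "All immunogenicity analyses will be descriptive". Section 9.3.2.1 plans no hypothesis test, and Table 2 in Section 3 lists GMT and GMFR as endpoints but not the GMT ratio.

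**The concern.** Stratified randomization forces near-balance on dose count and site. Where those factors predict the outcome, the true sampling variance of the group difference falls. A linear model without them still counts their contribution as residual noise, so its SE describes a trial randomized without strata. The group difference is not biased, but its SE is too large and the nominal 95% CI covers more than 95% of the time.

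Adjusting for Day 0 titer removes only what the strata share with baseline titer. Dose count could also affect the size of the booster response from a given starting titer, and site could carry population differences.

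The GMT ratio is the only model-based comparison of the two vaccines in the protocol. Section 9.1 says the sample size was not set by power, so the estimate and its CI are what a reader receives.

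**Working it through.** **The plan's own figures.** Section 9.1 gives only adverse event detection probabilities for 200 per group. They reproduce: 1 - 0.95^200 = 0.99996 (stated as above 99.9%) and 1 - 0.99^200 = 0.8660 (stated 86.6%). Neither bears on titers, and no figure for CI width is given.

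**Inputs from the protocol.** 400 participants, 1:1; up to 25 sites, so 400/25 = 16 per site; strata are dose count by site; the planned model is group plus Day 0 titer.

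**Assumptions, because the protocol gives no figures.** Three dose-count levels (40/40/20%), 25 sites of unequal size, permuted blocks of 4 within site by dose count, baseline SD 0.5 log10, slope 0.6, and variance after baseline 0.16 (SD 0.4 log10). The strata explain a share of that variance, varied from 0 to 15%, with 70% of the share from dose count and 30% from site. The percentage narrowing does not depend on the SD.

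**Analytic check.**
- Planned half-width ≈ t × SD × 2/√N = 1.966 × 0.4 × 2/20 = 0.0786 log10.
- Narrowing if the whole share is removed = 1 - √(1 - share), which is 1.0, 2.5, 5.1 and 7.8% for shares of 2, 5, 10 and 15%.

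**Simulation, 6,000 trials per row, n = 400.** Mean CI half-width in log10:

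| Share | Planned | + dose | + dose + random site | Narrowing, dose | Narrowing, dose + site | Planned coverage |
|---|---|---|---|---|---|---|
| 0% | 0.0787 | 0.0787 | 0.0785 | 0% | 0.3% | 95.1% |
| 2% | 0.0788 | 0.0782 | 0.0779 | 0.7% | 1.1% | 95.4% |
| 5% | 0.0787 | 0.0774 | 0.0768 | 1.7% | 2.5% | 95.2% |
| 10% | 0.0786 | 0.0758 | 0.0747 | 3.5% | 4.9% | 95.8% |
| 15% | 0.0786 | 0.0744 | 0.0728 | 5.3% | 7.5% | 96.1% |

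Ratios of the rounded half-widths agree with the narrowing columns to about 0.1 point. The Monte Carlo SE of coverage is about 0.3 points, so only the last two rows are clearly above 95%. Adjusted-model coverage is 94.5 to 95.6% throughout.

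**Is the SE really too large?** At a 10% share the planned estimate has empirical SD 0.0385 against a mean model SE of 0.0400; at 15%, 0.0379 against 0.0400. The implied coverage is 2Φ(1.96 × 0.0400/0.0385) - 1 = 95.8% and 2Φ(1.96 × 0.0400/0.0379) - 1 = 96.1%, as simulated. The adjusted model's implied SE at 10% is about 0.0747/1.966 = 0.038. So the change is mostly in the reported SE and little in the estimate.

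**On the ratio scale.** At a 10% share and a ratio of 1.0, the planned CI is 10^±0.0786 = 0.83 to 1.20, and the dose-plus-site CI is 10^±0.0747 = 0.84 to 1.19.

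**Participant equivalents of the reported width.** If the whole share is recovered, 400/(1 - share) - 400 = 21 at 5% and 44 at 10%. For dose count alone, 400 × ((0.0787/0.0774)² - 1) ≈ 14 and 400 × ((0.0786/0.0758)² - 1) ≈ 30.

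**Smaller analysis set.** Section 9.2.4 makes the per-protocol set depend on strain, assay and visit. If about 340 are evaluable (85%, assumed), narrowing for shares of 5, 10 and 15% is 1.7, 3.5 and 5.3% with dose count, and 2.4, 4.8 and 7.3% with dose count and site.

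**Different assumptions.** A second simulation (1,500 trials per setting) used two dose levels, an even dose/site split and fixed site effects. The planned CI was 2.1% wider than the adjusted one at a 5% share, 4.8% at 10%, 11.2% at 20% and 18.8% at 30%. At zero share the planned CI was slightly the narrower (width ratio 0.996), which is the price of fixed site terms that explain nothing.

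**The case against.** Nothing here invalidates the analysis. The protocol never promises a stratified model, so the two sections do not strictly conflict, and a valid interval that may be a little wide is lost efficiency rather than error. The immunogenicity analyses are descriptive, and the ratio is not a listed endpoint. Section 9.3.2.1 also gives a between-arm difference in seroresponse, so the reader does not depend on this ratio alone. Day 0 neutralizing titer to the same strain already measures baseline immunity directly, and nothing in the protocol shows that dose count or site adds to it. The sizes are all assumed. The SAP, not seen here, may add the terms.

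Most of this stands, and it sets the weight of the point: the gain is conditional, small and on the cautious side. It does not remove the point. The protocol chose dose count as a stratification factor and counts it as part of baseline immunity. It also states the model in full, so the covariates are not simply left open. Leaving the factors out protects nothing, since adding dose count costs essentially no precision even when it is not prognostic. The objection to site has some force at about 16 participants per site, and the fix allows for it.

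**Conclusion.** The mismatch is on the face of the protocol, and the direction of its effect is certain: no bias, and a conservative CI if the strata are prognostic beyond Day 0 titer. Whether they are, and by how much, cannot be learned from the protocol. For assumed shares up to 15% of the remaining variance, the planned interval gives away at most about 5% of its width for want of dose count and about 7.5% for want of dose count and site, with coverage up to about 96%. Shares of 20 to 30% would make it materially wider, but nothing in the protocol suggests values that large. No conclusion of the trial depends on this interval. This is a low-priority improvement, worth making because it is almost free.

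**What to change.** In Section 9.3.2.1, or in the SAP as a documented change, regress log Day 28 titer on vaccine group, log Day 0 titer and number of prior mRNA doses, taken as randomized and entered as a categorical term. Add site as a random intercept, or pool small sites. Back-transform the adjusted group difference to give the GMT ratio and its CI. Most of the gain comes from dose count under the 70/30 split assumed above; if site is left out, say so and give the reason.

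Settle this before the Day 28 extract, when Section 9.5 unblinds the sponsor at participant level, so that the choice of covariates cannot be called data-driven. The cost is one sentence. Both factors are already recorded for randomization, and sample size, visits and conduct are unaffected.

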9.3.2.2 Analysis of Secondary Immunogenicity Endpoints

For the secondary immunogenicity endpoints of NAb response against the Omicron XBB.1.5 strain over time, analyses will be performed using the Per-Protocol (PP) Analysis Set and the Neutralization Assay Subset. NAb GMTs to the Omicron XBB.1.5 strain and 95% CIs are summarized at Day 0, 90, and 180. NAb GMFR (compared to Day 0) and SRR to the Omicron XBB.1.5 strain and 95% CIs are summarized at Day 90 and 180.

For the secondary immunogenicity endpoints of IgG antibody levels against the Omicron XBB.1.5 strain over time, analyses will be performed using the Per-Protocol (PP) Analysis Set and the Anti-S Protein IgG Serology Subset. IgG GMEUs to the Omicron XBB.1.5 strain and 95% CIs are summarized at Day 0, 28, 90, and 180. IgG GMFR (compared to Day 0) and SRR to the Omicron XBB.1.5 strain and 95% CIs are summarized at Day 28, 90 and 180.

Summary statistics used to evaluate secondary immunogenicity objectives are summarized by vaccine group. There is no formal evaluation of statistical hypotheses.

9.3.2.3 Analysis of Exploratory Immunogenicity Endpoints

For the exploratory immunogenicity endpoints of NAb and IgG antibody responses against the ancestral (Wuhan) strain over time, analyses will be performed using the Per-Protocol (PP) Analysis Set, and within the Neutralization Assay Subset and the Anti-S Protein IgG Serology Subset respectively. NAb GMTs and IgG GMEUs to the ancestral (Wuhan) strain with corresponding 95% CIs are summarized at Day 0, 28, 90, and 180. NAb and IgG GMFR (compared to Day 0) and SRR with corresponding 95% CIs are summarized at Day 28, 90 and 180. The endpoints will be analyzed by vaccine group.

For the exploratory immunogenicity endpoints of antibody responses in a hACE2 receptor binding inhibition assay against the Omicron XBB.1.5 and ancestral (Wuhan) strains over time, analyses will be performed using the Per-Protocol (PP) Analysis Set and the hACE2 Receptor-Binding Inhibition Assay Subset. Serum hACE2 GMTs to the Omicron XBB.1.5 and ancestral (Wuhan) strains with corresponding 95% CIs are summarized at Day 0, 28, 90, and 180. hACE2 GMFR (compared to Day 0) and SRR to the Omicron XBB.1.5 and ancestral (Wuhan) strains with corresponding 95% CIs are summarized at Day 28, 90 and 180. The endpoints will be analyzed by vaccine group.

Mucosal IgA-mediated hACE2 receptor inhibition assay responses to the Omicron XBB.1.5 and ancestral (Wuhan) strains will be summarized using the PP Analysis Set and the Mucosal hACE2 Receptor-Binding Inhibition Assay Subset. GMTs to the Omicron XBB.1.5 and ancestral (Wuhan) strains with corresponding 95% CIs will be summarized at Day 0 and Day 28. GMFR (compared to Day 0) and SRR with corresponding 95% CIs will be summarized at Day 28.

The other exploratory Immunogenicity analyses will be defined in the SAP.

9.3.3 Other Exploratory Analyses

The other exploratory analyses will be defined in the SAP.

9.4 Other Statistical Considerations

9.4.1 Population Analysis

9.4.1.1 Disposition and Protocol Compliance

The number of participants consented, randomized/enrolled, and vaccinated will be presented by vaccine group for the All Randomized Participants Analysis Set.

The number (percentage) of participants in the All Randomized Participants Analysis Set, FAS, Safety Analysis Set, and PP Analysis Set for the primary endpoint only who have completed the study up to the time of pre-planned analyses (including EOS for the final analysis) will be summarized by vaccine group.

The number (percentage) of participants who discontinue the study prior to EOS and the reason for discontinuation (eg, AE, investigator decision, lost to follow-up, non-compliance, etc.) will be presented by vaccine group.

The number (percentage) of participants with major protocol deviation(s) recorded throughout the study will be summarized by vaccine group and protocol deviation category.

9.4.1.2 Demographics and Baseline Characteristics

Baseline demographic and background characteristics (eg, age, gender, ethnicity, race, height, weight, and BMI [derived]) will be summarized by vaccine group for the FAS, Safety, and PP Analysis Sets. Frequencies and percentages will be presented for categorical variables. Continuous variables will be summarized using descriptive statistics (total number of participants, mean and standard deviation, median, minimum, and maximum).

Medical history will be coded using MedDRA terms. Baseline medical history recorded at Screening will be summarized by the study vaccine group and by MedDRA SOC/PT for all participants in the Safety Analysis Set. Within each SOC and PT, the number and percentage of participants with at least one medical history event will be presented, respectively. Multiple events within a given SOC and PT for a participant will be counted once.

The characterization of baseline immunity will be summarized, to include tabulation of PCR and anti-N results at Day 0, the brand(s) of mRNA vaccine previously received, the number of doses received, and the length of the interval between last mRNA vaccine and study investigational vaccine.

9.4.1.3 Listings of Population Analysis data

Listings of all data used for analysis of population parameters will be created.

9.5 Planned Interim Analyses

A formal interim analysis will be carried out when the complete data is available to evaluate the primary endpoint. A set of secondary and exploratory endpoints will also be analyzed at this time, dependent on the availability of data. The database extract is expected to include immunogenicity data and safety data through Day 28. An independent statistics organization or the internal statistics team will perform the analysis and receive unblinded data at the time of analyses, following final determination of participant exclusions from analysis populations and database extract. At the time of Day 28 data extract with receipt of the randomization list, the Sponsor will be unblinded at the participant level to prepare for regulatory submissions.

9.6 Specified Analyses for Independent Data Monitoring Committee Review

Data surrounding suspected cases of myocarditis/pericarditis will be provided to the appointed Central Cardiac Adjudication Committee as needed

9.7 Procedures for Reporting Changes to the Planned Analysis

Changes to the analyses or analysis methods specified in the protocol will be documented in the SAP and in the clinical study report.

10 ETHICAL CONSIDERATIONS

10.1 Good Clinical Practice

The investigator agrees that the study will be conducted according to the principles of ICH E6(R2). The investigator will conduct all aspects of this study in accordance with all national, state, and local laws or regulations. The study will be conducted in compliance with the protocol, current GCP guidelines – adopting the principles of the Declaration of Helsinki – and all applicable regulatory requirements.

Prior to study initiation, the protocol and the informed consent documents will be reviewed and approved by the sponsor (or designee) and an appropriate ethics committee. Any amendment to the protocol or consent materials must also be approved by the study sponsor (or designee) and IRB and must be submitted/notified to the regulatory authority, as required, before they are implemented.

10.2 Ethics Review

Prior to the start of the study, the investigator is responsible for ensuring that the protocol and consent form have been reviewed and approved by a relevant IRB. The IRB shall be

appropriately constituted and perform its functions in accordance with ICH GCP and local requirements as applicable.

The IRB shall approve all protocol amendments (except for logistical or administrative changes), written informed consent documents and document updates, participant recruitment procedures (eg, advertisements), written information to be provided to the participants, IB, available safety information, information about payment and compensation available to participants, the investigator's curriculum vitae and/or other evidence of qualifications and any other documents requested by the IRB and Regulatory Authority (Competent Authority) as applicable.

